## 1 INTRODUCTION

Oral surgical procedures of any kind, from the extraction of a retained third molar to the rigid internal fixation of a mandibular fracture, may cause postoperative complications such as edema, trismus, and pain and interfere with the quality of life of patients. These aspects are important physiological responses but when observed at high intensity and duration, they may harm this critical period of surgical recovery.

No consensus in the literature allows defining a gold-standard protocol as postoperative conduct but most surgeons try to control the complication factors with drug therapies, from analgesics to anti-inflammatory drugs (steroidal or not). Overall, there is an underestimating of non-pharmacological maneuvers such as an effective instruction on the need for absolute rest and oral cavity hygiene, as well as cryotherapy, which is a common approach in the health field although often used empirically. The topical application of ice reduces the temperature of the skin and its adjacent tissues by 2 to 4 cm in depth, resulting in cold-induced neuropraxia and decreasing the threshold of nociceptor activation and the speed of conduction of nerve pain signals. This consequentially reduced blood flow through vasoconstriction, which may decrease the intensity of the inflammatory response of soft tissues to trauma.

The benefits of cryotherapy are not a consensus in the literature and this situation is often justified by the lack of a solid and effective treatment protocol, although the most used approach is applying ice to the region every 30 minutes in the first days. This conflict in the evidence can be seen in publications with results indicating that cryotherapy has no significant influence on edema and trismus, while other aspects report a positive increase in pain relief and other postoperative symptoms. The major unknown is still the actual influence of this therapy on pain levels.

Considering the extensive use of cryotherapy in third molar surgeries and the lack of agreement of scientific findings on its effectiveness, the present study evaluated whether the use of ice has a beneficial potential capable of reducing the intensity and duration of pain, as well as reducing edema and trismus and improve the quality of life.

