### 4.1 SAMPLE CALCULATION

The sample size was calculated based on a previously published study, which adopted a significance level of 5% ( $p < 0.05$ ), a statistical power of 90%, and a margin of error of 5%, resulting in a required sample size of 40 surgical sites. In the baseline study, pain perception during local anesthesia was compared between acupressure and cryotherapy using a split-mouth design involving 20 patients. Similarly, the present study employed a split-mouth design, with procedures performed on 20 patients, yielding a total of 40 surgical sites.

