#### 4.8 STATISTICAL ANALYSIS

Data normality was assessed using the Kolmogorov–Smirnov test. Parametric analyses were applied to compare groups (control side vs. test side) and postoperative time points (from day 0 to day 7). Continuous variables, including pain intensity (VAS scores), maximum mouth opening (mm), and facial edema (mm), were expressed as means  $\pm$  standard deviation (SD).

A two-way repeated-measures analysis of variance (ANOVA), followed by Fisher's least significant difference (LSD) post hoc test, was used to evaluate the main effects of time and treatment, as well as their interaction, for pain intensity, trismus, and edema. Pain reports were also qualitatively analyzed based on the frequency distribution of pain categories (no pain, mild pain, moderate pain, and severe pain) for both groups.

Associations between pain intensity and trismus or edema were assessed using Pearson's correlation coefficient. Trismus and edema were additionally evaluated using the formulas (Baseline – Postoperative) and (Postoperative – Baseline), respectively. Qualitative data related to quality of life were presented as percentages.

All statistical analyses were performed using SPSS software (version 20.0; IBM Corp., Armonk, NY, USA). Statistical significance was set at  $P < 0.05$ .

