### 5.3 EDEMA

Time significantly affected postoperative edema ( $F_{(2,32)} = 10.34$ ,  $p < 0.001$ ), whereas treatment ( $F_{(1,16)} = 0.516$ ,  $p = 0.48$ ) and the interaction between factors ( $F_{(2,32)} = 1.533$ ,  $p = 0.23$ ) did not.

Both groups exhibited greater edema on postoperative day 2 compared with baseline (Group A:  $123.0 \pm 5.1$  vs.  $126.2 \pm 7.8$ ,  $p = 0.02$ ; Group B:  $123.1 \pm 7.1$  vs.  $126.3 \pm 7.5$ ,  $p = 0.005$ ). No significant differences were observed between baseline and postoperative day 7 in either Group A ( $123.0 \pm 5.1$  vs.  $126.1 \pm 7.8$ ;  $p = 0.86$ ) or Group B ( $123.1 \pm 7.1$  vs.  $123.5 \pm 8.7$ ;  $p = 0.71$ ), indicating resolution of edema by the end of the evaluation period in both groups (Table 4).

[figure not shown]

Table 4: Average of edema values on days 0, 2 and 7 post-op.

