A strong association was also observed between higher pain intensity reports and increased requests for rescue medication in the control group. These results indicate that failure to use cryotherapy may increase reliance on pharmacological interventions to manage postoperative discomfort, which could otherwise be mitigated through a simple and low-cost intervention such as ice pack application for 30 minutes over a 12-hour period. Therefore, the proposed cryotherapy protocol can be considered a safe and effective approach that enhances postoperative predictability, facilitates complication control, and promotes greater patient engagement in self-care.

Trismus represents a multifactorial postoperative response influenced by surgical trauma, including osteotomy, extracellular fluid extravasation, tissue hemorrhage, and muscle fiber incision. Given the simultaneous occurrence of these factors, significant benefits of cryotherapy are not expected before consolidation of the inflammatory response, which explains the absence of intergroup differences during the first 72 postoperative hours. However, when comparing immediate postoperative measurements with those obtained on postoperative day 7, the control

group exhibited significantly greater mouth opening limitation (Table 2), indicating a longer duration of trismus. This finding is supported by the statistically significant correlation between pain intensity and trismus observed exclusively in the control group (Table 3), suggesting that higher pain levels are associated with prolonged mouth opening restriction. These results were further corroborated by the quality-of-life questionnaire, which revealed greater difficulty in mouth opening among control participants.

Edema did not show statistically significant differences between groups (Table 4), consistent with previous reports. It is hypothesized that superficial ice application may be insufficient to significantly reduce edema due to its limited penetration into deeper muscular and facial tissue planes, thereby restricting its vasoconstrictive effects.

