## 7 CONCLUSION

Postoperative cryotherapy was effective in reducing pain intensity and duration, decreasing the need for rescue medication, and shortening the period of mouth opening limitation after mandibular third molar extraction. This intervention also improved patients' perception of recovery and contributed to a more predictable postoperative course. However, cryotherapy did not demonstrate a significant effect on postoperative edema.

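### The edema comparison is reported only as non-significant p-values, and limited ice penetration is offered as its sole explanation, although the day-2 estimate is too imprecise to exclude a reduction of roughly half

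*Combined protocol and SAP*

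**What the plan says.** Section 4.7 lists local edema among the outcomes, measured before surgery and on days 2 and 7. Section 4.8 defines edema change as postoperative minus baseline and plans a two-way repeated-measures ANOVA at the 5% level.

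Section 5.3 reports treatment F(1,16) = 0.516, p = 0.48, and treatment by time F(2,32) = 1.533, p = 0.23. It adds within-side comparisons: "Both groups exhibited greater edema on postoperative day 2 compared with baseline". The difference between the two sides is never given as an estimate with an interval.

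The Discussion notes the lack of a significant difference and continues: "It is hypothesized that superficial ice application may be insufficient to significantly reduce edema". The reason given is that cold reaches too little of the deeper muscle and facial planes, which limits vasoconstriction. The Introduction says that topical ice "reduces the temperature of the skin and its adjacent tissues by 2 to 4 cm in depth". The Conclusion says that "cryotherapy did not demonstrate a significant effect on postoperative edema".

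Section 4.1 takes its sample size from a published study with "a statistical power of 90" per cent, "resulting in a required sample size of 40 surgical sites". In that study "pain perception during local anesthesia was compared between acupressure and cryotherapy using a split-mouth design involving 20 patients". Section 4.1 gives no effect size, SD or power for edema.

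**The concern.** A non-significant p-value shows that the data did not separate the two sides. It does not show how large a difference remains compatible with them. When the text moves from such a p-value to a biological reason for failure, with no interval and no mention of precision, readers may take edema as a settled negative with a known cause.

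Two features make this more likely here. The trial was not sized for edema, and three of the 20 planned patients were lost, leaving 17 pairs. The penetration idea also sits uneasily with the Introduction, where cooling to a depth of centimetres and vasoconstriction are the rationale for using ice. No tissue temperature, depth or blood flow was measured. At stake is what the trial may conclude on one of its four outcomes.

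**Working it through.** **Printed figures.** The upper tail of F gives p = 0.483 for F(1,16) = 0.516 and p = 0.231 for F(2,32) = 1.533. Both agree with section 5.3.

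**Inputs (section 5.3, n = 17 pairs).**
- Group A: 123.0 at baseline, 126.2 on day 2, change +3.2 mm, p = 0.02.
- Group B: 123.1 at baseline, 126.3 on day 2, change +3.2 mm, p = 0.005.
- Difference in change, A minus B: 3.2 − 3.2 = 0.0 mm.

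**Assumptions.** The within-side p-values are two-sided paired t tests with 16 df. The correlation r between a patient's two changes is not reported, so a range is shown.

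**Standard errors of change (change ÷ t).**
- A: 3.2 / 2.583 = 1.24 mm.
- B: 3.2 / 3.252 = 0.98 mm.

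**Interval for the difference.** SE = √(1.24² + 0.98² − 2r × 1.24 × 0.98); half-width = 2.12 × SE.

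| r | SE (mm) | 95% half-width (mm) | Share of 3.2 mm |
|---|---|---|---|
| 0 | 1.58 | 3.35 | 105% |
| 0.3 | 1.33 | 2.82 | 88% |
| 0.5 | 1.13 | 2.40 | 75% |
| 0.7 | 0.89 | 1.89 | 59% |

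Half of the control-side swelling is 1.6 mm. It stays inside the interval until r reaches about 0.79.

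**Interval for the ratio.** The last column treats 3.2 mm as known, but it is itself an estimate. Fieller's method allows for this. With θ = B change ÷ A change, the limits solve (3.2 − 3.2θ)² = 2.12² × (0.98² − 2θr × 1.24 × 0.98 + θ² × 1.24²). With unrounded SEs, the lower root for θ is 0.30, 0.37, 0.43 and 0.53 at r = 0, 0.3, 0.5 and 0.7. The largest compatible reduction, 1 − θ, is therefore about 70%, 63%, 57% and 47%. Setting θ = 0.5 in the same equation gives r of about 0.64, above which an exact halving is excluded on this scale.

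**Ice side alone.** 3.2 ± 2.12 × 0.98 gives about 1.1 to 5.3 mm, which excludes zero swelling.

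**A route set aside.** The error mean square can also be backed out of the interaction F. The A minus B differences at the three visits are −0.1, −0.1 and 2.6 mm. They give an interaction mean square of 20.7, an error mean square of 20.7 / 1.533 = 13.5, SE = √(4 × 13.5 / 17) = 1.78 mm and a half-width of about 3.6 mm. Because the first two differences are equal, the whole interaction sum of squares comes from day 7, where the Group A value is doubtful. The route also assumes sphericity, so the conclusion does not rest on it.

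**Why the day-7 value is doubtful.** Group A is printed as 123.0 ± 5.1 against 126.1 ± 7.8 with p = 0.86. The SD of change cannot exceed 5.1 + 7.8 = 12.9 mm. So t is at least 3.1 / (12.9 / √17) = 0.99, and p can be at most about 0.34.

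**The case against.** The text is hedged. The Discussion labels the penetration idea a hypothesis, and the Conclusion says only that a significant effect was not demonstrated. Nowhere is equivalence claimed. This stands: a reader might infer that the authors assert no effect, and the wording does not support that. What hedging the mechanism does not do is disclose the imprecision, which is the more immediate explanation.

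The day-2 point estimate is exactly zero, and r is unknown. Both operations were in the same patient with the same surgeon, so r could be high and the interval narrower. This also stands, which is why a range is shown.

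A tempting stronger reading is that the data cannot tell no effect from complete or near-complete prevention, since at r = 0 the half-width (3.35 mm) exceeds the control-side swelling (3.2 mm). That does not hold. It treats the control-side swelling as fixed and ignores significant swelling on the ice side. A true difference of 3.2 mm with at least 1.1 mm on the ice side would need at least 4.3 mm on the control side, which is not complete prevention.

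A second tempting reading is that the 2 to 4 cm statement contradicts the Discussion. The documents give no depth for the planes in question, and the Introduction acknowledges publications that found no significant influence on edema. It is a tension in wording, not a demonstrated contradiction.

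One could also say that the larger edema problems are the day-7 p-value and the Abstract, which reports full regression only in Group B while section 5.3 reports resolution in both. Those do need settling first, but they do not remove the need for an interval.

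**Conclusion.** The point holds as a reporting and interpretation weakness that is cheap to correct. The edema result is inconclusive, not evidence of no effect. On day 2 the difference in change is 0.0 mm, with a 95% half-width of about 3.4 mm (r = 0), 2.4 mm (r = 0.5) or 1.9 mm (r = 0.7), against 3.2 mm of control-side swelling. A reduction of roughly half, or a comparable worsening in millimetres, is not excluded. Complete prevention is not supported.

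These figures rest on the printed day-2 means and p-values, on reading those p-values as paired t tests, and on assumed correlations. An interval from the patient data would replace them.

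**What to change.** 1. Check the Group A day-7 edema value and its p-value against the source data, and bring the Abstract and section 5.3 into agreement on which side had resolved by day 7.
2. In section 5.3, report the paired between-side difference in change from baseline on days 2 and 7, each with its 95% CI, from the patient data. Section 4.8 already defines the change score.
3. In sections 5.3 and 7, state that the edema result is inconclusive, and in section 5.3 that the stated sample-size basis was not edema.
4. In section 6, present limited penetration as one untested possibility beside low precision, and reconcile its wording with the cooling depth and vasoconstriction rationale in section 1.

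The cost is a paired estimate per visit from existing data and a few sentences. The downside is that a clean negative becomes an inconclusive result.

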## 7 CONCLUSION

Postoperative cryotherapy was effective in reducing pain intensity and duration, decreasing the need for rescue medication, and shortening the period of mouth opening limitation after mandibular third molar extraction. This intervention also improved patients' perception of recovery and contributed to a more predictable postoperative course. However, cryotherapy did not demonstrate a significant effect on postoperative edema.

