## ABSTRACT

Third molar extraction is a common oral surgical procedure often associated with postoperative pain, edema, and functional limitation. Effective postoperative management plays a key role in minimizing morbidity and promoting patient comfort. Strategies such as cryotherapy may contribute to improved recovery and quality of life after surgery. **Objective:** to investigate the effects of cryotherapy on postoperative outcomes (pain intensity, edema, trismus and quality of life) following mandibular third molar extraction. **Materials and Methods:** This study was designed as a randomized split-mouth clinical trial. The sample consisted of 17 patients (34 mandibular third molars with equivalent levels of impaction) who underwent bilateral surgical extraction. The surgical sites were allocated into two groups according to postoperative care: Group A (control side—without cryotherapy) and Group B (test side—with postoperative cryotherapy using ice packs). All intraoperative and postoperative procedures, instructions, and medications were identical for both groups. Patients were evaluated for pain intensity, trismus severity, presence of edema, and quality of life for up to seven days postoperatively (D7). The evaluator was aware of the postoperative intervention applied. Repeated-measures ANOVA was used to analyze each outcome variable, and associations between continuous variables were assessed using Pearson's correlation test. Statistical significance was set at 5% ( $P < 0.05$ ). **Results:** Overall, postoperative pain intensity was lower in patients who received cryotherapy. Group A reported significantly higher pain intensity on postoperative days 1 and 3. No signs of trismus were observed in Group B at the end of the follow-up period, whereas Group A presented restricted mouth opening at D7. Both groups exhibited edema on postoperative day 2 (D2); however, complete regression of edema by D7 was observed only in Group B. Additionally, a significant association between pain intensity and trismus severity was identified in Group A at D7. Quality-of-life assessment revealed significant differences in three questionnaire items favoring Group B, including greater perceived improvement, better mouth opening, and reduced difficulty sleeping. **Conclusion:** The findings suggest that postoperative cryotherapy is effective in reducing pain intensity and trismus following mandibular third molar extraction. Moreover, this physical therapy modality appears to enhance pain tolerance and patients' self-perceived healing.

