## 2 OBJECTIVES

### 2.1 GENERAL OBJECTIVE

To investigate the effects of cryotherapy on postoperative outcomes (pain intensity, edema, trismus and quality of life) following mandibular third molar extraction

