## 4.7 STUDY VARIABLES

The outcome variables of this study were postoperative pain, trismus, local edema, and changes in quality of life following mandibular third molar extraction. Postoperative assessments were performed by the research team, consisting of two calibrated surgeons and one supervising professor, on postoperative days 0 (day of surgery), 2, and 7. The following evaluation protocols were applied:

a) Pain assessment: postoperative pain was assessed using a visual analog scale (VAS– APPENDIX C) ranging from 0 to 10, in which 0 represented no pain, 1–3 mild pain, 3.1–6 moderate pain, and 6.1–10 severe pain. Patients completed the scale at home daily until postoperative day 7.

b) Trismus assessment: trismus was evaluated by measuring maximum mouth opening with the patient seated and the tragus–ala plane parallel to the ground. Patients were instructed to open their mouths three consecutive times, and the mean value was recorded. Measurements were obtained as the interincisal distance in millimeters using a measuring tape. In the absence of maxillary or mandibular incisors, the occlusal edges were used as reference points. Measurements were recorded on postoperative days 0, 2, and 7.

c) Edema assessment: facial edema was measured using the method described by Gabka and Matsumura. Three linear facial measurements were obtained in millimeters with a measuring tape: tragus to pogonion, tragus to oral commissure, and lateral canthus to mandibular angle. The mean of these three measurements was calculated to quantify edema. This assessment was performed preoperatively and on postoperative days 2 and 7.

d) Quality of life assessment: quality of life was evaluated using a questionnaire adapted from the OHIP-14 (APPENDIX D), consisting of 14 dichotomous (yes/no) questions addressing daily functional limitations. The questionnaire included items related to chewing and swallowing ability, dietary changes, alterations in taste, mouth opening, voice changes, speech intelligibility, facial appearance, sleep disturbances, and ability to perform work-related activities. The questionnaire was provided to participants on the day of surgery and completed on postoperative days 0, 2, and 7. At the conclusion of the evaluation period following the second intervention, participants also answered the question: “Which intervention did you perceive as resulting in greater postoperative improvement?”

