## 6 DISCUSSION

Cryotherapy was effective in reducing both the intensity and duration of postoperative pain episodes, as well as shortening the period of mouth opening limitation. Additionally, its use in the postoperative period resulted in a reduced need for rescue medication and a greater patient-perceived improvement over time. These findings support the consolidation of a cryotherapy protocol, contributing to a more predictable postoperative course and improving the management of postoperative complications.

As shown in Table 1, differences in mean pain scores during the first 72 postoperative hours (from day 0 to the end of day 2) appear to be related to the lack of consolidation of the inflammatory response under pharmacological analgesia alone. Pain modulation was only stabilized after postoperative day 3 in both groups, as also reported by Sukegawa et al. However, cryotherapy demonstrated a

beneficial synergistic effect when combined with analgesic medication, resulting in lower pain scores during this critical period. In contrast, analgesic therapy alone was insufficient to adequately control pain in the control group, which exhibited two distinct peaks in pain intensity at 24 and 72 hours postoperatively.

The benefit of cryotherapy for the test group was particularly evident between postoperative days 2 (the last day of analgesic medication) and 3 (the first day without medication). During this transition, pain levels increased in the control group and remained consistently higher than those observed in Group B, even during the consolidation phase of the inflammatory response. These findings suggest that the greater differences in pain intensity are directly associated with the absence of cryotherapy in the control group, despite the use of analgesics.

Pain severity distribution over the seven postoperative days further reinforced these findings (Graphics 1 and 2). Proportionally, extractions performed without cryotherapy were associated with a significantly higher likelihood of moderate-to-severe pain. From a clinical perspective, the absence of cryotherapy increased the probability of requiring rescue medication. This observation is particularly relevant for patients with systemic diseases who already require complex pharmacological regimens, increasing the risk of drug interactions, as well as for individuals susceptible to medication dependence, for whom minimizing drug exposure is essential.

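### Sections 6 and 7 conclude that cryotherapy shortened pain duration, but no duration measure is defined and no between-side duration estimate or test is reported, although the daily VAS diary would allow one.

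*Combined protocol and SAP*

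**What the plan says.** **The question.** The Introduction asks whether ice is "capable of reducing the intensity and duration of pain". The general objective (2.1) names pain intensity but not duration, and the specific objectives (2.2) do not mention duration.

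**The outcome.** Section 4.7 says: "The outcome variables of this study were postoperative pain, trismus, local edema, and changes in quality of life following mandibular third molar extraction". Pain is a 0 to 10 VAS, and "Patients completed the scale at home daily until postoperative day 7". No number of days with pain, last day of pain or time to a threshold is defined.

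**The analysis.** Section 4.8 plans a two-way repeated-measures ANOVA on pain intensity, with LSD post hoc tests, and a descriptive frequency distribution of pain categories. Nothing addresses duration.

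**The result.** Section 5.1 reports effects of treatment, time and their interaction on mean VAS, between-side differences on days 1 and 3, and category percentages for each side.

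**The conclusion.** The Discussion opens with "Cryotherapy was effective in reducing both the intensity and duration of postoperative pain episodes", and section 7 repeats it: "Postoperative cryotherapy was effective in reducing pain intensity and duration, decreasing the need for rescue medication". Neither statement is hedged. The abstract adds that "this physical therapy modality appears to enhance pain tolerance".

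**The concern.** How intense pain is and how long it lasts are separate properties. A diary in which every score is halved has half the mean and exactly as many painful days. A lower mean on particular days is therefore not evidence of a shorter course, and the reported tests compare only means.

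Duration is one of the things the Introduction sets out to learn, and it is answered with an unqualified yes. A reader of section 7 would take that as a tested finding on the same footing as intensity. The readable text gives no effect in days, no measure of its uncertainty and no definition of when pain counts as over.

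The tolerance remark in the abstract is a smaller matter. Tolerance is a different construct from reported intensity, and no section defines or measures it.

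**Working it through.** **1. Reproduce the reported pain tests (section 5.1).**
- Treatment: F(1,16) = 5.063 gives p = 0.0389 (stated 0.039).
- Treatment by time: F(7,112) = 2.689 gives p = 0.0130 (stated 0.013).

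Both reproduce. The degrees of freedom fit 17 patients and 8 daily scores: 17 − 1 = 16, 8 − 1 = 7, and 16 × 7 = 112. The quantity tested is mean VAS. The follow-up contrasts (day 1: 3.59 vs 2.12; day 3: 3.24 vs 1.29) are also differences in mean VAS.

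**2. Recover the counts behind the category percentages.** There are 17 patients × 8 days (day 0 to day 7) = 136 reports per side.

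| Category | Control | Count of 136 | Cryotherapy | Count of 136 |
|---|---|---|---|---|
| None | 29.4% | 40 | 44.1% | 60 |
| Mild | 50.0% | 68 | 47.8% | 65 |
| Moderate | 16.9% | 23 | 7.4% | 10 |
| Severe | 3.7% | 5 | 0.7% | 1 |
| Total | | 136 | | 136 |

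Every percentage is recovered to one decimal. Apart from 29.4% (5/17), none fits a denominator of 17, so these are pooled patient-day reports and not shares of participants.

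**3. Convert to days per patient.**
- Any pain: (136 − 40)/17 = 96/17 = 5.65 for control; (136 − 60)/17 = 76/17 = 4.47 for cryotherapy. Difference: 20/17 = 1.18 days.
- Moderate or severe: 28/17 = 1.65 versus 11/17 = 0.65. Difference: 17/17 = 1.00 day.

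The direction favours cryotherapy. The counts do not show whether pain ended earlier or came and went.

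**4. Could the 1.18 days be distinguished from zero?** A paired t-test uses t = 1.18/(SD/√17) on 16 degrees of freedom, where SD is that of the within-patient difference. The documents do not give it, so a range is assumed. The 95% CI is 1.18 ± 2.12 × SD/√17.

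| Assumed SD (days) | t | p | 95% CI (days) |
|---|---|---|---|
| 1 | 4.85 | 0.0002 | 0.66 to 1.69 |
| 2 | 2.43 | 0.028 | 0.15 to 2.20 |
| 2.5 | 1.94 | 0.070 | −0.11 to 2.46 |
| 3 | 1.62 | 0.125 | −0.37 to 2.72 |
| 4 | 1.21 | 0.243 | −0.88 to 3.23 |

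The break-even SD is 1.176 × √17/2.120 = 2.29 days. Below it the difference is significant at 5%; above it, it is not.

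**5. Pain tolerance.** Nothing can be computed, because no variable corresponds to it.

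**The case against.** The strongest reply is that the trial did collect what it needs. Scores were recorded daily to day 7 for each side, the category table was planned and reported, and it points to fewer painful days with cryotherapy. The Discussion also says that control-side pain stayed higher after day 3. Table 1 and Graphics 1 and 2 are not visible in the text available here and may show more for the later days.

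Much of this stands, and it rules out some stronger readings.

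- A reader might infer that duration was answered with no data at all. That is wrong: the diary bears directly on it. What is missing is a definition and a paired comparison.
- A reader might infer that, because the text names only days 1 and 3 as different, a shorter course is refuted. That does not follow. If pain settled before day 3 on one side and after it on the other, the difference would appear on day 3, where one is reported. With 17 pairs, non-significance on later days would not show equal duration either.
- A reader might count tolerance as a second failed headline. It appears once, hedged, in the abstract, and belongs to neither the question nor the objectives.

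The reply does not rescue the conclusion. Higher control scores after day 3 are again a statement about level, and the category table is pooled over patients and untested.

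**Conclusion.** The duration claim in sections 6 and 7 is unsupported as reported, but it is not shown to be false. The documents imply a difference of about 1.18 days with any pain in favour of cryotherapy. Whether chance can be excluded depends on an SD that is not given: the p-value runs from 0.0002 to 0.24 over an assumed SD of 1 to 4 days, with the break-even near 2.3.

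This rests on three assumptions: that the percentages are pooled reports over days 0 to 7 (supported by the exact fit to 136), that no pain means a VAS of 0, and that a paired t-test is adequate for a count limited to 8 days. The statement that no duration result exists is limited to the readable text.

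The intensity result does not depend on this point, and its F-tests reproduce. The tolerance phrase needs only a wording correction.

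**What to change.** 1. Derive one duration measure per patient and side from the diary already held: the number of days from day 0 to day 7 with VAS above 0. Give the last day with VAS above 3 as supportive only. Fixing a single main measure avoids choosing among definitions after seeing the results.
2. Report the mean paired difference, control minus cryotherapy, with its SD and 95% CI, and label it post hoc.
3. Word sections 6 and 7 to match that interval. If the analysis is not done, remove duration from both sentences, so that they claim reduced intensity only.
4. In either case, delete the phrase on enhanced pain tolerance from the abstract's conclusion.

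The cost is one paired analysis of existing data and a few words of text. The duration statement may or may not survive it. Even if it does, it remains a post hoc result limited to the seven-day diary.
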